**Informed Consent:**

Patients will first be introduced to this research following completion of their New Patient Intake (a set of online questionnaires completed by all MSAS patients upon referral to our sleep center). They will be pre-screened for eligibility prior to their diagnostic PSG. Following MD review and interpretation of the diagnostic PSG, qualifying research candidates will be scheduled to meet with a research coordinator to discuss their results in detail (SDB, hypoxia, sleep fragmentation, sleep architecture, etc.). The research protocol will be introduced by discussing the relationship between SDB and sleep fragmentation as well as treatment credibility of PAP therapy. By reviewing his or her study and discussing the research protocol at the same time, we can illustrate how nighttime awakenings due to SDB are fragmenting sleep and discuss how this study will test whether or not treating these breathing events with different types of PAP may change their insomnia.

Study protocol is thoroughly discussed with patient and they are educated on insomnia as it relates to SDB. Patients will be informed that we are comparing two devices to find out which is more

effective in treating SDB events in patients with chronic insomnia and what impact this treatment has on decreasing insomnia. Once they have signed the informed consent form, they will be randomized into a treatment group but will have the option to try the other treatment at the end of the study.

Patients will meet with [name] at this point to undergo a brief airway exam and are given the opportunity to ask [name] any remaining questions. Candidates who do not qualify for the study following diagnostic PSG will continue to receive care in the sleep center as appropriate.

### **Study Procedure Summary (4 Phases)**

#### **Phase 1: Pre-Screening Steps and Enrollment in the Study**

These steps may take place over the course of several days to complete all pre-screening and enrollment encounters.

##### **First Encounter (by phone)**

1. Patient seeks treatment at sleep center for chronic insomnia and completes Web Intake (full medical history and sleep history).
2. Physician reviews medical history, including concomitant medications, demographic information, and collects weight and height to assess BMI.
3. [name] informs research coordinator of potential eligibility.
4. Research coordinator contacts patient to complete pre-screening survey.
  - a. Patient informed whether they have potential eligibility based on pre-screen.
  - b. Patient informed of [name] recommendation for proceeding according to standard of care, regardless of research interests.

##### **Second Encounter (in person, at sleep lab)**

1. Patients expressing interest in the protocol will be scheduled for and will complete the Diagnostic PSG.
  - a. [name] completes interpretation and recommendations per standard of care following a diagnostic study.
  - b. If OSA or UARS positive (and confirmed by independent scorer), patient is scheduled for full explanation of research project and signing of informed consent form.
  - c. If OSA or UARS negative, patient will be informed and will proceed with standard clinical care.

##### **Third Encounter (in person, at sleep lab)**

1. PSG results discussion with research coordinator
2. Confirmation that the patient meets I/E criteria
3. Patient reviews and signs informed consent form
4. [name] conducts airway exam and answers patient questions.
5. Subject randomized to treatment arm
6. Completion of special baseline questionnaires
  - a. One week Sleep Diary (see below) with Global Morning Rating of Nightly Sleep
  - b. Insomnia Impairment Index

- c. Fatigue Severity Scale
- d. Intake Supplement

7. Schedule Titration #1

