### ***Protocol***

#### **Abstract:**

[figure not shown]
As presented in the in-depth Background material, emerging research strongly indicates the need for an RCT to evaluate the role of PAP therapy in the treatment of chronic insomnia. This study, succinctly summarized in the following two flow charts (A. Patient Encounters; B. Patient Timetable) proposes this project to test standard CPAP therapy versus a more advanced form of CPAP therapy known as adaptive servo-ventilation (ASV). During a 14-16 week period, two groups of approximately 25 patients each will use either CPAP or ASV, and their specific sleep outcomes and related variables will be tracked daily or every two weeks to provide data for a final comparative analysis between the two groups. The summary of endpoint objectives (page 10) following the two flow charts describes the primary and secondary outcomes for this study.

Flowchart A: Patient Encounters in Protocol Steps. This chart describes the entry of the patient into the study after confirmation of the diagnosis of SDB.

[figure not shown]
Flowchart B: Patient Timetable and Protocol Steps. This chart describes estimated time commitment for each participant once the diagnosis of SDB is confirmed.

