**Inclusion and Exclusion Criteria:**

## Inclusion criteria:

1.  $\geq 18$  years old
2. Primary complaint of insomnia when presenting at clinic
3. Diagnosis of moderate to severe insomnia through the Insomnia Severity Index (ISI) with a score  $\geq 15$
4. Meet diagnostic criteria of Insomnia Disorder (per American Academy of Sleep Medicine)
5. Diagnosis of SDB, either OSA as determined by an AHI  $\geq 5$  events/hour or UARS with a RDI  $\geq 15$  events/hour and AHI  $< 5$  events/hour
6. Naïve to treatment for sleep-disordered breathing (SDB), including CPAP, APAP, ASV; mandibular repositioning devices (MRDs), and any other nasal or oral therapy with a primary indication of treating SDB
7. Able to fully understand study information in English and sign informed consent

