### **Power Analysis, Sample Size Data Analysis**

#### **Power Analysis and Sample Size:**

Based on our description in the background (see page 6), our work with ASV anticipates an effect size of at least 1.40 to 1.50 change in insomnia severity with ASV PAP therapy. Whereas, based on our clinical experience we presume that the effect of CPAP on insomnia would yield an effect size range between 0.50 and 0.70. Thus, the average net effect between ASV and CPAP use would be ~0.80 effect size. Using a resource specific to clinical research(77)in order to calculate power and sample size estimates, we used a beta of .90 for two tailed significance testing at .05 which arrived at 26 patients per group, or a total sample of 52. Therefore, using the less stringent criteria of beta .80, we believe our sample size allotments of 25 per group or 50 total should prove more than sufficient for this protocol.

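### OSA and UARS patients are mixed in a trial of about 50, but neither the described allocation nor the analysis accounts for SDB type, which adds avoidable noise to the CPAP-ASV contrast in AHI change

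*Combined protocol and SAP*

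**What the plan says.** **Allocation.** The Third Encounter lists "Subject randomized to treatment arm" as one step, after eligibility is confirmed and consent is signed. The Synopsis and the Informed Consent section add only the two arms and that consent comes first. The readable text states no sequence generation, ratio, blocks, strata or concealment, and rules none of them out. The two flow charts are not reproduced. On size, the Abstract says that "two groups of approximately 25 patients each will use either CPAP or ASV".

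**Entry.** Inclusion criterion 5 begins "Diagnosis of SDB, either OSA as determined by an AHI" and sets the OSA threshold at 5 events/hour. The alternative is UARS, with RDI of at least 15 and AHI below 5. SDB type is settled at the Second Encounter, before consent and allocation. That step reads "If OSA or UARS positive (and confirmed by independent scorer", followed by scheduling of the consent visit.

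**Analysis.** AHI and RDI are secondary endpoints. The Data Analysis section specifies a repeated measures ANOVA with a group-by-time test, first for ISI and then in similar fashion for the breathing indices. It names no covariate or stratum.

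**The concern.** Two patient types that differ in baseline AHI by definition enter one small comparison. The factor that separates them is measured and independently checked before allocation, and nothing described then uses it.

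Analysing change does not remove the link. AHI cannot go below zero, so the largest possible fall is the baseline value. For a UARS patient that is less than 5/h; for an OSA patient it is at least 5/h and may be far more. If one arm happens to hold more UARS patients, its mean AHI fall is smaller under the same device performance. Even when the arms are balanced, the gap between types sits in the error term of the group-by-time test and widens the interval for the device contrast.

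At stake are the precision and readability of the AHI comparison, which is the direct evidence on whether one mode controls breathing events better than the other.

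**Working it through.** **1. The plan's own size.** Inputs from Power Analysis and Sample Size: the effect, "the average net effect between ASV and CPAP use would be ~0.80 effect size"; and the error rates, where beta stands for power, "we used a beta of .90 for two tailed significance testing at .05". The stated result is 26 per arm (52 in all). With n per arm = 2(z₁₋α/₂ + z_power)²/d²:
- power .90: 2(1.960 + 1.282)²/0.64 = 32.8, so 33 (34 by t-test), not 26;
- power .80: 2(1.960 + 0.842)²/0.64 = 24.5, so 25 (26 by t-test).

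The figure of 26 therefore matches power .80. That is a separate matter. The adopted 25 per arm gives power 0.807 (normal) or 0.791 (t-test), which is the base used below.

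**2. Arm size, if allocation were simple 1:1 for 50 patients.** P(20:30 or worse) = 2·P(Bin(50, ½) ≤ 20) = 0.203; P(18:32 or worse) = 0.065. T-test power is 0.791 at 25:25, 0.775 at 20:30 and 0.758 at 18:32, and 0.783 averaged over all splits. The loss is about 1 to 3 points.

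**3. SDB mix.** The documents give no expected UARS share, so 20-40% is assumed. Given arm size m, the number of UARS patients in that arm is hypergeometric; simple allocation averages this over m ~ Bin(50, ½).

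| UARS among 50 (assumed) | P(share differs ≥ 20 points), simple | Same, arms held at 25:25 |
|---|---|---|
| 10 (20%) | 0.081 | 0.074 |
| 15 (30%) | 0.136 | 0.217 |
| 20 (40%) | 0.155 | 0.148 |

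Equal arm sizes without strata do not solve the problem. The middle row is higher at 25:25 because 15 UARS patients can split 10:5, which is exactly 20 points.

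**4. Shift in the AHI contrast.** Shift = (difference in UARS share) × (mean fall in OSA − mean fall in UARS). With assumed falls of 3/h in UARS and 10-25/h in OSA, a 20-point difference gives 0.20 × (10 − 3) = 1.4/h up to 0.20 × (25 − 3) = 4.4/h, with no device difference.

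**5. Gain from a model term.** Let p be the UARS share and k the gap in mean AHI fall between types, in units of the within-type SD. Adjusting for type multiplies the standard error by about 1/√(1 + p(1 − p)k²). The documents do not give k. With k assumed from 1 to 2:
- k = 1: reduction of 7% (p = 0.2) to 10% (p = 0.4);
- k = 1.5: 14% to 19%;
- k = 2: 22% to 29%.

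**6. RDI.** UARS requires RDI of at least 15, while OSA requires AHI of at least 5 and sets no RDI minimum. A UARS patient can enter with a higher RDI than a patient with mild OSA, so step 4 does not carry over.

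**7. ISI.** Nothing in the documents links SDB type to ISI response. If type shifted ISI change by an assumed 0.3-0.8 SD, a 20-point difference would move the contrast by 0.20 × 0.3 = 0.06 to 0.20 × 0.8 = 0.16 SD. The planned effect is 0.80 and the standard error is √(2/25) = 0.28. If the shift went against ASV, t-test power would fall from 0.79 to between 0.73 and 0.60.

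**The case against.** **The method may already be restricted.** A reader might infer that patients are allocated by simple randomisation without blocks or strata. The documents do not say so. They are silent, and planned groups of about 25 fit blocked allocation as well as coin-tossing. This stands: the probabilities in steps 2 and 3 are conditional. The missing analysis term does not depend on it.

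**Chance imbalance is not bias.** This also stands. The type I error already covers it, so the gain is in precision and interpretability. It would be wrong to say that the ISI result is distorted, since the documents give no prognostic effect of SDB type, or that RDI is affected by construction. Arm-size imbalance is minor.

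**Adjustment alone would do most of the work.** Largely true for AHI, which is why the analysis change comes first below. Stratifying adds some protection against a poor split at little cost. A case could also be made for another stratum, such as baseline ISI, in a trial whose initial analysis is ISI. SDB type is preferred because its link to a listed endpoint is built into the entry rule.

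**Blocks make assignments easier to guess.** Valid. A research coordinator sets each device to its assigned mode (Set-up), and that role also meets candidates before allocation. Someone who tracks past assignments in a stratum and always guesses the arm that is behind is right in m + 2^(2m−1)/C(2m, m) − ½ of the 2m places in a block: 1.5/2 = 75% for size 2, 2.83/4 = 71% for size 4 and 4.1/6 = 68% for size 6, against 50% under simple allocation. This is a reason to avoid blocks of 2. It is a cost of the remedy, and a list held elsewhere does not fully remove it.

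**Conclusion.** The point holds for AHI. SDB type fixes a baseline difference in that endpoint and is known before allocation, but neither the described allocation nor the stated model uses it. Under simple allocation, the chance of a 20-point difference in UARS share is about 0.08 to 0.155. The resulting shift is 1.4-4.4/h. Adjusting would cut the standard error of the AHI contrast by roughly 7-29%. These figures rest on an assumed UARS share of 20-40%, assumed AHI falls of 3/h and 10-25/h, and k of 1 to 2; the documents supply none of them.

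It is a loss of precision in a secondary endpoint, not a bias. The effect on ISI is unknown, and no mechanical effect on RDI follows. The improvement is worth making because the factor is already collected.

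**What to change.** **Data Analysis.** In the breathing-index models, add SDB type and its interaction with time, or use an ANCOVA of the follow-up value with baseline AHI as covariate. The interaction is needed because a main effect of type alone shifts the average level and leaves the change untouched. Add SDB type by time to the ISI model.

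**Third Encounter, randomisation step.** State a 1:1 allocation stratified by SDB type as confirmed at the Second Encounter, in randomly varying blocks that avoid size 2 (for example 4 and 6). The list should be held by someone without patient contact, and each assignment released only after eligibility and consent are recorded. With blocks up to 6, each stratum can be out by at most 3 patients. The worst arm split is then 22:28 (power 0.802 against 0.807, normal approximation), and the UARS share can differ by at most about 3/25 = 12 points. With blocks of 4 only, the limits are 23:27 and about 8 points.

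**Cost.** One or two model degrees of freedom, minor administration, and some predictability within blocks because staff know the mode. The sample size does not change.

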In our work and that of Guilleminault and colleagues,(68-74) emerging research suggests complex insomnia represents a much more common condition than previously anticipated in contrast to the wealth of research that focuses on the psychophysiological basis of chronic insomnia. Some treatment research, while involving only small samples, points to the potential for sleep breathing to play a larger role in the etiology of chronic insomnia in a sizeable proportion of patients. Most of these studies have been anecdotal or cases series with a few randomized controlled studies.(68-74) Despite the weakness in many of these designs, particularly a lack of clarity in some protocols as to selection bias and diagnostic criteria for insomnia disorders, all the studies showed improvements in insomnia symptoms subsequent to treatment for sleep-disordered breathing regardless of the therapy mode (positive airway pressure therapy, oral appliance therapy, nasal/oral airway surgery, bariatric surgery, and nasal dilator strips).

Two of the more rigorous studies included our randomized controlled trial assessing the impact of nasal dilator strips (NDS) and SDB education on insomnia severity and SDB symptoms in chronic sleep maintenance insomniacs.(69) We found patients using NDS and receiving SDB education had significantly improved insomnia, sleep quality, and life satisfaction compared to a control group. The other study, a randomized crossover prospective study by Guilleminault et al. comparing CBT-I and surgical treatment for OSA in 30 complex insomnia patients,(74) showed surgical intervention was more successful in improving insomnia than CBT-I alone. Although patients receiving initial treatment with CBT-I also showed increased TST, once these patients completed the surgical arm of the study their TST was further increased and SOL was significantly decreased.

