## **Summary of Endpoint Objectives:**

### **Primary Endpoint objectives:**

- Change in insomnia severity from baseline to 4 months as measured by the Insomnia Severity Index (ISI)
- Sleep Diary sleep quality rating (8 point Likert scale)
- Global Morning Rating of Nightly Sleep (0-100% scale)
- Change in prospective sleep log data for insomnia parameters (SOL, WASO, SE)

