## Exclusion criteria:

1. Primary complaint of sleep-disordered breathing or issues with apneas during sleep
2. Severe respiratory disorder or severe sleep disorder such as restless leg syndrome (RLS), idiopathic hypersomnia, or narcolepsy
3. BMI  $> 30$  kg/m^2
4. Epworth Sleepiness Scale (ESS) score  $\geq 10$
5. Frequent napping behavior, such as a few times a week or more
6. Anticipated changes to start or stop sedative or psychotropic medications during the course of the trial.
7. Medical history of congestive heart failure (CHF) or other potentially unstable cardiac disease as well as chronic lung diseases or other debilitating medical conditions that manifest as more prominent in the patient's health compared to their sleep complaints.
8. Daily use of opiate medications
9. Known contraindications to PAP therapy as listed in the indication for use
10. Requires a CPAP (fixed) pressure  $> 20$  cm H2O
11. Inability to comply with study procedures

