### **Follow-up Visits**

Participants will return every 2 weeks following their titration study for a follow-up clinic appointment conducted by sleep technologist with availability of [name] for relevant Q&A with patient. The following will be completed at each follow-up appointment:

1. Outcomes: Subject completes the following questionnaires:
  - a. Validated research instrument for tracking insomnia: ISI
  - b. Sleep related impairment: ESS, VAS-F, VAS-S, III, FSS, SDB-6
  - c. Quality of Life/Impairment: FOSQ-10, QLESQ, HSCL
  - d. PAP Therapy Tracking Tools: AEC, NOSE-8
  - e. Change Tracking Tool: PGA (Insomnia, Sleep Quality, Fatigue, Sleepiness, Energy level)
2. Data, download from the VPAP Adapt.
  - a. Usage
  - b. AHI, flattening %
3. Review device usage. Address concerns or questions including:
  - a. Progress and experiences with PAP
  - b. Benefits or lack thereof
4. Review sleep diary.
5. Determine if the subject has had any adverse events or adverse device effects.
  - a. Troubleshoot as needed

**Summary:** Following initial titration, the following steps will reoccur for the remainder of the protocol (refer to initial flow chart to see repetition of steps):

- Patients return on weeks 2 and 4 for Follow-up visits
- On week 6 they repeat titration process and complete Follow-up visit surveys and downloads
- Return on weeks 8 and 10 for follow-up appointments
- Return on week 12 for a final titration

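### No ISI is scheduled between intake and PAP, so the baseline appears to be the qualifying score; within-arm ISI change would then include regression to the mean, while the ASV-versus-CPAP test is unaffected

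*Combined protocol and SAP*

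**What the plan says.** All places are in the combined protocol and SAP.

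- **Endpoint.** The first item under Primary Endpoint objectives is "Change in insomnia severity from baseline to 4 months as measured by the Insomnia Severity Index (ISI"). The visit that supplies the baseline is not named there or elsewhere.
- **Selection on the same scale.** Inclusion criterion 3 requires "Diagnosis of moderate to severe insomnia through the Insomnia Severity Index (ISI) with a score" of at least 15. Exclusion criterion 4 removes patients with an "Epworth Sleepiness Scale (ESS) score" of 10 or more; the ESS is a secondary endpoint.
- **Intake.** The Informed Consent section describes the New Patient Intake as "a set of online questionnaires completed by all MSAS patients upon referral to our sleep center". It does not list the instruments.
- **Before treatment.** Item 6 of the Third Encounter, "Completion of special baseline questionnaires", contains the one-week diary with the Global Morning Rating, the III, the FSS and the Intake Supplement. It follows item 5, randomisation.
- **Next ISI.** The Follow-up Visits section lists "Validated research instrument for tracking insomnia: ISI" at each two-weekly visit, when the patient is on PAP.
- **Education.** Before consent and randomisation the coordinator reviews the sleep study with the patient so that "we can illustrate how nighttime awakenings due to SDB are fragmenting sleep".
- **Use of the change.** The Synopsis plans a comparison of baseline scores with those at four months. Purposes 2 and 3 (Purpose & Clinical Impact) concern the impact of PAP on insomnia severity and its role as a new therapeutic pathway.
- **Primary test.** Data Analysis specifies a repeated measures ANOVA for the group-by-time interaction.

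**The concern.** Patients admitted because a score is high tend to score lower when measured again, with or without treatment. If the qualifying ISI is also the baseline, that fall is counted as change on PAP.

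The protocol has no arm in which such a fall could be seen, since the Background argues against sham PAP. Any statement about what PAP as such does for insomnia must therefore rest on the within-arm change. The ESS has the mirror problem: patients are selected for low scores, so later scores would tend to rise.

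The education session falls between the intake score and PAP and may add to the ISI fall. The Background reports of the site's own nasal dilator strip (NDS) trial: "We found patients using NDS and receiving SDB education had significantly improved insomnia, sleep quality, and life satisfaction compared to a control group".

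**Working it through.** **Which ISI is the baseline?** The follow-up battery contains the ISI, ESS, VAS-F, VAS-S, III, FSS, SDB-6, FOSQ-10, QLESQ and HSCL. Of these, only the III and FSS are in the Third Encounter set. The others have a pre-treatment value only if one was taken at intake or at a step the text does not itemise. The Questionnaires section also has the PGA rate change against intake. Both facts point to intake as the source. The alternative, that no baseline ISI is scheduled at all, would be worse.

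**Plan's own figures.** The plan gives no figure for drift. The Background gives two pre-post ISI falls with effect sizes:
- 16.8 − 9.7 = 7.1, d = 1.40, implied SD 7.1/1.40 = 5.07
- 19.0 − 11.9 = 7.1, d = 1.50, implied SD 7.1/1.50 = 4.73

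The presumed CPAP effect of 0.50 to 0.70 (Power Analysis and Sample Size) is then 0.50 × 4.73 = 2.4 to 0.70 × 5.07 = 3.6 points.

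**Regression to the mean, ISI.** For a normal source population with mean m, SD s and retest correlation r, selected at 15 or more (cut 14.5):

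spurious fall = (1 − r) × s × φ(z)/(1 − Φ(z)), with z = (14.5 − m)/s.

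The values of m and r are assumptions; the documents give neither. Example: m = 14, s = 5.1, r = 0.6 gives z = 0.10, ratio 0.86, and 0.4 × 5.1 × 0.86 = 1.8 points. Each cell below shows s = 4.7 and s = 5.1.

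| m | r = 0.6 | r = 0.7 | r = 0.8 | r = 0.9 |
|---|---|---|---|---|
| 14 | 1.63, 1.76 | 1.22, 1.32 | 0.81, 0.88 | 0.41, 0.44 |
| 16 | 1.14, 1.27 | 0.86, 0.95 | 0.57, 0.63 | 0.29, 0.32 |
| 18 | 0.74, 0.85 | 0.55, 0.64 | 0.37, 0.43 | 0.18, 0.21 |

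The range is about 0.2 to 1.8 points. Against the 7.1-point falls: 0.18/7.1 = 3% to 1.76/7.1 = 25%. In SD units the fall is 0.04 to 0.35. Against the presumed CPAP effect that is 0.04/0.70 = 6% to 0.35/0.50 = 70%. With m = 16 and r = 0.7 it is 0.18/0.70 = 26% to 0.19/0.50 = 38%. With m = 12, s = 5, r = 0.6 the fall reaches 0.4 × 5 × 1.14 = 2.3 points.

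**ESS.** The mirror formula with cut 9.5, assumed mean 8 to 10, SD 4.5 and r 0.7 to 0.9 gives a spurious rise of 0.3 to 1.2 points. Every input except the cut is assumed.

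**Effect on the randomised comparison.** A simulation of 5,000 trials with 25 per arm used m = 16, s = 5, r = 0.75, an illustrative 1-point education effect and a true 3-point fall in both arms.
- Within-arm fall: 4.76 from the qualifying score, 3.00 from a repeat score. The excess of 1.76 is the 1 point assigned to education plus 0.76 of regression.
- Between-arm difference: 0.02 and 0.01 when the truth is 0; 4.02 and 4.02 when the truth is 4.
- SD of the between-arm difference when the truth is 0: 1.28 and 1.31.

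**How much a repeat would remove.** The simulation treats the errors in the two pre-treatment scores as independent. Phase 1 says that pre-screening and enrolment may take several days, and the ISI looks back two weeks, so the two scores may cover partly the same nights. If intake correlates 0.9 with the repeat and 0.7 with month 4 (assumed), the share of regression left after re-baselining is (0.9 − 0.7)/(1 − 0.7) = two-thirds.

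**The case against.** The strongest reply is that the confirmatory result is untouched. The hypothesis is ASV against CPAP, the test is the group-by-time interaction, and selection and education both precede randomisation and act equally on the arms. That stands. A reader might infer that the primary comparison is biased; the design and the simulation both say it is not. Nor is the test shown to be noisier with the intake score as baseline: the simulated SDs are nearly equal.

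Second, the point is partly an inference from silence. The intake instruments and the pre-screening survey are not itemised. Item 2 of the Third Encounter, the eligibility check, might include a repeat ISI. Flow charts A and B are not in the text reviewed. So it cannot be stated as fact that the intake ISI is the only pre-treatment score. What stands is that the text schedules no other and does not name the baseline visit.

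Third, the size depends on assumptions. A reader could take the 2.3-point corner, set it against 2.4 points, and conclude that nearly all of the presumed CPAP effect is artefact. That corner needs a source mean of 12, which the ISI tiers class as subthreshold, in patients whose primary complaint is insomnia, together with r = 0.6. At 16.8, the mean of the first Background sample (PAP failures, so a different population), SD 5 gives 1.06, 0.79, 0.53 and 0.26 points for r = 0.6, 0.7, 0.8 and 0.9. The SDs are themselves back-solved from effect sizes whose denominators are not stated, one of them from a sample restricted to ISI above 15.

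Fourth, the dilator-strip trial tested strips and education together, so it gives no size for education alone.

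Finally, the plan attaches effect sizes to the interaction test and does not say that they will be reported per arm.

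**Conclusion.** The point holds for the within-arm change and only there. As written, the baseline ISI appears to be the intake score that qualified the patient. The four-month fall within each arm would then contain roughly 0.2 to 1.8 points of regression to the mean, assuming a normal source population with mean 14 to 18, SD about 5 and retest correlation 0.6 to 0.9 (up to 2.3 if the source mean is as low as 12). This is a minor part of a 7.1-point fall but could be a substantial part of a CPAP effect of 2.4 to 3.6 points. The 7.1-point falls are themselves uncontrolled pre-post changes, so they are a yardstick and not a true effect.

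The ESS would drift upward by an amount that rests wholly on assumptions. Education may add to the ISI fall by an unknown amount. The change should be made because purposes 2 and 3 lean on the within-arm change; the primary test does not depend on it.

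**What to change.** 1. State which visit supplies the baseline for every change endpoint.
2. Add the ISI and ESS to the Third Encounter, with any other outcome scale otherwise collected only at intake (possibly FOSQ-10, QLESQ, HSCL, VAS-F, VAS-S and SDB-6). Complete them after the sleep-study discussion and consent but before randomisation; item 6 now follows item 5.
3. Use intake ISI and ESS for eligibility only, without reapplying the thresholds, and define baseline as the Third Encounter value.
4. Report the change from intake to the Third Encounter, with the interval between the two scores, as the drift seen without PAP.
5. State that the correction is partial when the scores are less than two weeks apart. A score taken on the day of the education session also looks back on nights before it, so it cannot remove a later effect of education on sleep. Within-arm change should be interpreted with both limits in view.

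The cost is protocol wording and a few minutes of questionnaires at an existing visit. Some patients will have a baseline ISI below 15, and the reported within-arm change will look smaller.
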